v2.0 16APR 2019	16APR 2019	
Amendment No.01
 
Number the inclusion and exclusion criteria.
 
Refine the Chinese translation of “.....and allow central over read turn over before randomization” as inclusion criteria to clarify the central reading result for endoscopy need to be ready before randomization.
 
Clarify subjects who had inadequate response, loss of response or intolerance to conventional treatment (immune-suppressants or corticosteroids) could be included, whether the subjects previously exposed to biological therapy or not.
 
Clarify the definition of treatment naïve subjects in exclusion criteria. Correct the typos to clarify the exclusion criteria for biological therapy use, “subjects receiving interferon therapy within 12 weeks prior to baseline and anti-TNFα therapy/other biological therapies within 12 weeks prior to baseline” will be excluded, instead of 8 weeks, in order to keep consistency with Section 5.2 Inclusion Criteria. Clarify subjects with hematopoietic disorders at screening should be excluded.
 
Correct the typos in Table 1 in Section 5.12 Time and Event Table, and the footnotes to ensure the procedures are consistent with subject selection criteria. Clarify chest X-ray to be performed if no chest X-ray or CT scan available within 3 months of Visit 1 instead of 6 months in footnote 2. Typo correction to clarify the follow up visit is not a phone-call contact and clarify any SAEs will be recorded from the time of consent in footnote 7. Allow T-Spot as an alternative test for TB infection screening. Clarify only serum β-Human Chorionic Gonadotrophin (β-HCG) is requested for pregnancy testing at screening visit and urine test is to be done from baseline. Clarify concurrent medication assessment should be done in Follow up/EW visit, in order to keep consistent with Section 6.6 Concomitant Medications. Clarify the early withdrawal visit should

Version Number	Version Date	Summary of Changes
		
be done within 2 weeks after last dose/decision of withdrawal rather than after 2 weeks of last dose/decision of withdrawal in footnote 11. FSH test is listed in the table to confirm postmenopausal status at screening.
 
Provide oral steroids tapering guidance in Section 6.6.1 Permitted Concomitant Medications and refine the Chinese translation of oral steroids permission
 
Remove the time period of “within baseline”, to clarify the prohibition is throughout the duration of the study to avoid confusion in Section 6.6.2 Prohibited Medications. And add live vaccines immunization as prohibited medications.
 
Clarify that the images/video clips of endoscopy will be sent to central lab for central reading in Section 7.2.5 Mayo Score Assessment.
 
Refine the Chinese translation of the intervals of 3 ECGs in Section 7.3.2, to clarify “Triplicate ECG measurements are collected at rate of 3 ECGs with 5 minutes between each.”.
 
Allow T-Spot test as an alternative test for TB infection screening according to local availability in Section 7.3.4 QuantiFERON test/or T-Spot test. And provide the guidance on initial QFT-G/or T-Spot is indeterminate.
 
Correct typos in Table 3 in Section 7.3.5 Clinical Laboratory Testing.
 
Update the reference.

v3.0 30JUL2019	30JUL 2019	
Amendment No.02
 
Update Section 4.1 Study Design, Section 4.2 Discussion of the design and Section 5.12 Time and Event Table, to revise the screening period to -28 days to -1 day prior to baseline, based on the feasibility of the clinical procedure in each country.
 
Update Section 5.2 Inclusion Criteria, to clarify the subjects deemed by the treating physician as having

Version Number	Version Date	Summary of Changes

1.1 Rationale

Ulcerative Colitis (UC) is a debilitating disease resulting in high morbidity and severely affect patients' quality of life. Patients with UC will experience periods of remission and flare up. It is a disease affecting the colon, characterized by altered bowel habit, bloody diarrhea, abdominal pain, weight loss and anaemia. The prevalence of UC is about 200/100,000 in the west compared to 50-60/100,000 in China or Japan. Its incidence has been higher in the West compared to the East. However, over the last decade, the prevalence has increased in the East. (1) The cause of UC remains unknown; it is thought to be closely linked to autoimmunity to large bowel mucosal. (2) UC can develop at any age, but peak incidence is between the ages of 20 and 30 years. It mainly affects the rectum, and a variable extent of the colon proximal to the rectum. Inflammation of the rectum is referred to as proctitis, and inflammation of the rectum and sigmoid as proctosigmoiditis. Symptoms of active disease or relapse include bloody diarrhoea, an urgent need to defaecate and abdominal pain.

Currently the only way to "cure" the disease is by total colectomy which is not without its risk and complication. The treatment goal in UC is to induce response in those in active stage and to continue maintaining remission, ultimately ensuring patients have minimal symptoms and good quality of life. Over many decades, these were achieved by applying oral and intravenous immune-suppressants. Conventional immune-suppressants treatments include oral glucocorticoids, mesalamine, and methotrexate. The introduction of biological treatment nearly two decades ago such as, anti-TNF α , a IgG monoclonal antibody has changed the treatment paradigm for moderate to severe UC over the last decade and has now become a gold standard. However, its use is still limited by its cost in some regions.

The understanding of cytokines and intracellular messenger pathway in UC has led to the discovery of Janus Kinase (JAK) enzymes, and their role in the activation of Signal Transducers and Activators of Transcription (STATs) via auto phosphorylation (3). The JAK-STATs pathway regulates the signaling of various interferon and interleukin which are implicated in the pathogenesis of UC. By blocking this pathway, it is thought that this immune-regulated inflammation could be halted, hence controlling the disease (4).

There are a number of Janus kinase (JAK) inhibitors currently under investigation for the treatments of immune-induced diseases, such as Rheumatoid Arthritis (RA), Psoriatic Arthritis, Psoriasis, Ulcerative Colitis, Crohn's Disease, and Ankylosing Spondylitis. These JAK inhibitors can be given orally, which could be an advantage compared to the intravenously given biological treatments. There is also an advantage of not having the risk of developing loss of response due to immunogenicity.

Tofacitinib, a 'pan-JAK inhibitor', blocking JAK3 and JAK1 and to a lesser extent JAK2 has been approved in the US for the treatment of RA. It has recently been approved for the treatment of Ulcerative Colitis in the US. Other JAK inhibitors with varying JAK selectivity profiles have already shown to be efficacious in RA, and some are under investigation for Ulcerative Colitis and Crohn's Disease indication. While inhibition of JAK1 and JAK3 contributed to the efficacy of RA treatment, inhibition of JAK2 may contribute to the safety concerns of anemia, and thrombocytopenia, by interfering with signaling through erythropoietin, thrombopoietin and colony-stimulating factors such as granulocytemacrophage colony-stimulating factor (5).

[REDACTED]

6

1.2 Objectives

The primary objective is to evaluate the efficacy of SHR0302 at 4mg once daily (QD), 8mg QD, and 4mg twice daily (BD) given orally compared to placebo in inducing clinical response in adult subjects with moderate to severe active Ulcerative Colitis at 8-week.

1.3 Study Design

This is an 8+8 weeks, randomized, double-blind, multi-center, placebo controlled, parallel group study to include adult patients with moderate to severe active Ulcerative Colitis. The study consists of an 8-week blinded treatment phase, followed by 8-week of blinded active arms extension phase. The primary endpoint is assessed at the end of treatment phase at week 8.

Eligible subjects will be randomized to either one of the 3 doses of active drugs or placebo in 1:1:1:1 ratio for 4mg QD, 4mg BD, 8mg QD and placebo group respectively for treatment phase. The total number of subjects to be randomized is 152. There will be a total of 9 outpatient clinic visits. Subjects randomized into placebo in treatment phase will also have a pre-assigned randomized treatment sequence for extension phase, which are 3 active groups (placebo -> 4mg QD, placebo -> 4mg BD, and placebo -> 8mg QD) in a 1:1:1 ratio. Subjects randomized to the active arms for treatment phase will remain in the same dose group in the extension phase.

At Visit 1 (screening), subject will be screened and if the subject meets the inclusion/exclusion criteria, the subject can be consented and enrolled into the study with a subject identifier number.

At Visit 2 (Day 0), subject will be randomized into the study if there is no further change to subject's criteria.

After randomization, the subject will be followed-up at week 1, week 4, and week 8, corresponding to Visit 3, Visit 4, and Visit 5 at treatment phase respectively. At Visit 5 (week 8) the primary endpoint assessment will be conducted. Following this treatment phase, subjects have the option to enroll into a further 8 weeks of active arms extension phase.

All subjects that have completed the initial 8 weeks (non-responders or responders) have the option to enter a blinded active arm 8-week extension phase according to the group they were randomized to for extension phase. All subjects have the option not enrolling into the extension phase after first 8 weeks of treatment. All subjects in the extension phase are followed-up for further 2 weeks until week 18 (last visit). Subjects who have completed the first 8-week of treatment phase, but decided not entering into extension phase are required to attend the 2-week follow-up visit. Early withdrawn subjects during the first treatment phase cannot enter the extension phase.

The total duration of the study participation, including extension and follow-up, will be approximately 18 weeks.

1.4 Study Endpoints

1.4.1 Primary Efficacy Endpoint

The percentage of subjects that achieve clinical response at week 8, defined as decrease from baseline in 9-point modified Mayo score of at least 2 points and at least 30%, with an accompanying decrease in the subscore for rectal bleeding of at least 1 point or absolute subscore for rectal bleeding of 0 or 1.

(Mayo Score is a scoring system designed to measure UC disease activity. It consists of 4 subscore, stool frequency, rectal bleeding, endoscopy score - findings of centrally read colonoscopy, and physician global assessment (PGA). Each graded from 0 to 3 with higher scores indicating more severe disease. These scores are summed up to give a total score from 0 to 12, where higher score indicate more severe disease.

9-point modified Mayo score is the Mayo score excluding physician global assessment (PGA)subscore, hence the maximum is 9 points and minimum 0 point

Partial Mayo score is the Mayo score excluding endoscopy subscore, hence the maximum is 9 points and minimum 0 point)

1.4.2 Secondary Efficacy Endpoints

- The percentage of subjects that achieve clinical remission per 9-point modified Mayo score at week 8, where stool frequency subscore ≤ 1 , rectal bleeding subscore of 0, and endoscopic subscore ≤ 1
- The percentage of subjects that achieve clinical remission at week 8 as per total Mayo score of 2 points or lower than 2, with no individual subscore exceeding 1 point and a rectal bleeding subscore of 0.
- The percentage of subjects that achieve endoscopic remission (mucosal healing) at week 8, defined by Mayo endoscopic subscore ≤ 1 point.
- Change from baseline in 9 point modified Mayo score at week 8.
- Change from baseline in total Mayo score at week 8.
- Change from baseline in partial Mayo score (Mayo score without endoscopy) at week 1, 4, 8, 9, 12 and 16.
- Change from baseline in the level of biomarkers CRP, faecal calprotectin.
- The systemic exposure of SHR0302 in steady state in Ulcerative Colitis patients (i.e. concentration and area under the curve).

1.4.3 Safety Endpoints

- To evaluate the safety and tolerability by laboratory parameters.
- To evaluate the safety and tolerability by collection of AE/SAE incidence
- To measure vital signs (blood pressure (BP), heart rate (HR), and body temperature)
- To measure subject's total lipid profile, which includes Triglyceride, LDL and HDL.
- To measure subject's thyroid profile: TSH, fT4 and fT3.
- 12 -lead ECG

2. Introduction

2.1 Background

Ulcerative colitis is an autoimmune disease resulting in the chronic inflammation of colon mucosal characterized by relapsing–remitting pattern. UC is a lifelong disease that is associated with significant morbidity. It can also affect patient's social and psychological wellbeing, if poorly managed. Current medical approaches focus on treating active disease to address symptoms, to improve quality of life, and thereafter to maintain remission. The treatment chosen for active disease is likely to depend on clinical severity, extent of disease and the patient's preference, and may include the use of aminosalicylates, corticosteroids or biological drugs. These drugs can be oral or topical (per rectum), and corticosteroids may be administered

intravenously in people with acute severe disease. Currently the only way to “cure” the disease is by total colectomy – the removal of the entire colon. This is a major surgery which carries risk and complications. Surgery is often reserved for those not responding to drug treatment.

The treatment goal in UC is to induce and maintain remission. Conventional treatments include oral glucocorticoids, mesalamine, and methotrexate. The introduction of biological treatment such as, anti-TNF α , a IgG monoclonal antibody has changed the treatment paradigm for moderate to severe UC over the last decade and has now become a gold standard. However, its use is still limited by its cost in some area.

The understanding of cytokines and intracellular messenger pathway in the pathophysiology of Ulcerative Colitis has led to the discovery of Janus Kinase (JAK) enzymes, and their role in the activation of Signal Transducers and Activators of Transcription (STATs) via auto phosphorylation. The JAK-STATs pathway regulates the signaling of various interferon and interleukin which are implicated in the pathogenesis of UC. By blocking this pathway, it is thought that this immune-regulated inflammation could be halted, hence controlling the disease (3,4).

There are a number of Janus kinase (JAK) inhibitors currently under investigation for the treatments of immune-induced diseases, such as Rheumatoid Arthritis, Psoriatic Arthritis, Psoriasis, Ulcerative Colitis, Crohn’s Disease, and Ankylosing Spondylitis. These JAK inhibitors can be given orally, which could be an advantage compared to the intravenously given biological treatments. Small molecule, unlike biological treatment, has no risk of developing loss of response due to immunogenicity.

A series of six horizontal black bars of varying lengths, decreasing from left to right. The bars are positioned at different vertical intervals, creating a stepped effect. The first bar is the longest and is located near the top. The second bar is shorter and is located below the first. The third bar is the shortest and is located below the second. The fourth bar is longer than the third and is located below the third. The fifth bar is longer than the fourth and is located below the fourth. The sixth bar is the longest bar in the series and is located below the fifth bar.

3. Objectives

3.1 Primary Objectives

The primary objective is to evaluate the efficacy of SHR0302 at 4mg, 8mg QD, and 4mg BD given orally compared to placebo in inducing clinical response in adult subjects with moderate to severe active Ulcerative Colitis at Week 8.

3.2 Secondary Objectives

The secondary objectives are;

- To evaluate the safety and tolerability of oral SHR0302 in subjects with moderate to severe ulcerative colitis.
- To evaluate the efficacy of oral SHR0302 in inducing clinical remission in subjects with moderate to severe ulcerative colitis.
- To evaluate the efficacy of oral SHR0302 in inducing mucosal healing in subjects with moderate to severe ulcerative colitis.
- To evaluate the change from baseline in the following biomarkers; CRP, fecal calprotectin.
- To further evaluate the efficacy of SHR0302 in maintaining remission.
- To characterize the pharmacokinetics of SHR0302 in moderate to severe active Ulcerative Colitis patients, and explore the correlation of exposure-response.

4. Investigational Plan

4.1 Study Design

See [Figure 1](#).

[figure not shown]

Figure 1. Study design diagram

4.2 Discussion of the design

This is a multi-national, multi-center, double-blind, randomized, placebo controlled phase II dose-ranging study to include 152 subjects with moderate to severe active ulcerative colitis. The study consists of an 8-week blinded treatment phase, followed by an 8-week active arms extension phase. Subjects will be screened between -28 days to -1 day before baseline visit (visit 2 at Day 0).

At the baseline visit, subjects with moderate-to-severe active ulcerative colitis, with a modified 9-point Mayo score of 5 to 9 points and endoscopic subscore of 2 to 3, and fulfilling all the inclusion/exclusion criteria will be randomized into one of the four treatment arms for the treatment phase; three active and one placebo; 4mg QD, 8mg QD, 4mg BD of SHR0302 or placebo. Subjects randomized into placebo in treatment phase will also have a pre-assigned randomized treatment sequence for extension phase, which are 3 active groups (placebo \rightarrow 4mg QD, placebo \rightarrow 4mg BD, and placebo \rightarrow 8mg QD) in a 1:1:1 ratio. Subjects randomized to the active arms for treatment phase will remain in the same dose group in the extension phase.

All the subjects will be stratified according to whether they have previously exposed to anti-TNF α /biological treatment. The double-blind treatment period will last for 8 weeks. Primary endpoint is collected at week 8. At the completion of treatment period, all subjects, responders or non-responders, have the option to enter a blinded active arms 8-week extension phase according to the group they were randomized to for the extension phase. All subjects are followed-up for further 2 weeks until week 18 (last visit). All the subjects have the option not enrolling into the extension phase after first 8 weeks of treatment. Early withdrawn subjects during the first treatment phase cannot enter the extension phase. The end-of-study is defined as the date of the last subject's last visit or the actual date of follow-up visit/contact, whichever is later.

5. Subject Selection and Withdrawal Criteria

5.1 Number of subjects

152 eligible subjects will be randomized to achieve an estimated 140 evaluable subjects in the study. The following eligibility criteria are designed to select subjects for whom protocol treatment is considered appropriate. All relevant medical and non-medical conditions should be taken into consideration when deciding whether a particular subject is suitable to participate in this study. Subject eligibility should be reviewed and documented by an appropriately qualified member of the investigator's study team before subjects are included in the study. Subject must be able to provide an informed consent to participate in this study at his own will.

5.2 Inclusion Criteria

Subjects must meet all of the following inclusion criteria to be eligible for enrolment into the study;

1. Male and Female subject age ≥ 18 and ≤ 75 years of age at randomization.
2. Active ulcerative colitis with a 9-point modified Mayo score of 5 to 9 points and endoscopic subscore of 2 to 3 (The duration of the time between endoscopy and baseline should not exceed 10 days and allow central over read turn over before randomization).
3. Subject should have at least three-month history of Ulcerative Colitis diagnosis at randomization.
4. Subjects deemed by the treating physician as having inadequate response, loss of response or intolerance to the conventional treatment (oral 5-ASA, immune-suppressants or corticosteroids), or previously exposed to anti-TNF therapy (e.g. infliximab, adalimumab) or other biological treatment (e.g. Vedolizumab) having discontinued the treatment for:
 - Infliximab: a minimum of 8 weeks prior to baseline
 - Adalimumab: a minimum of 10 weeks prior to baseline
 - Ustekinumab: a minimum of 14 weeks prior to baseline
 - Vedolizumab: a minimum of 17 weeks prior to baseline
 - For the other biological treatments, they should discontinue for a minimum of 5 half-lives prior to baseline.
5. If subjects are currently receiving the following treatment for UC, they are eligible for the study, provided they are on stable dose for the required period of time:
 - Oral 5 ASA or Sulfasalazine, stable dose for at least 2 weeks prior to baseline and during the study treatment period.

AND/OR

- Oral corticosteroids (prednisolone \leq 30mg/day or less or equivalent) stable dose for at least 2 weeks prior to baseline. This is not applicable to the subjects who have only exposed to 5-ASA previously as per inclusion criteria 4.

6. Subject must have no evidence of active, latent, or inadequately treated infection with *Mycobacterium tuberculosis* (i.e., tuberculosis [TB]), as defined by the following:

- A negative Mantoux Purified Protein Derivative (PPD) skin test result (\leq 5 mm of induration), or negative QuantiFERON TB Gold (QFT Gold test) /or T-Spot test performed within the 3 months prior to/within screening;

AND

- Subject must have a chest radiograph, taken within the 3 months prior to/within screening, and showing no changes suggestive of active TB infection.

AND

- Subject must have no history of either untreated or inadequately treated latent or active TB infection

7. All women of childbearing potential and all men must be willing to use at least one highly effective method of contraception from signing of informed consent, throughout the duration of the study, and for 1 month after last dose of study medication: (refer to [Section 5.4](#) for further details on contraception requirements for this study)
- Male subjects with a female partner of childbearing potential must be willing to use condom in addition to a highly effective contraceptive method.

8. Subjects who are willing and able to comply with the scheduled visits and treatment plan, laboratory testing and other study procedures.

9. Capable of providing a signed and dated informed consent form indicating the subject has been informed of all pertinent aspect of the study.

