5.3 Exclusion Criteria

Subjects presenting with any of the following will not be included in the study:

1. Diagnosis of indeterminate colitis, or clinical findings suggestive of Crohn's disease.
2. Subjects with ulcerative colitis, which is confined to a proctitis (distal 15 cm or less).
3. Treatment naïve subjects diagnosed with ulcerative colitis (without previous exposure to any of the following therapies for UC treatment: oral 5-ASA, corticosteroids, immune-suppressants, or biological treatments).
4. Subjects displaying clinical signs of ischemic colitis, fulminant colitis or toxic megacolon.

5. Subject who have had previous surgery as a treatment for ulcerative colitis or likely to require surgery during the study period.
6. Subjects who have evidence of pathogenic bowel infection. Subjects had *Clostridium difficile* or other intestinal infection within 30 days of screening endoscopy, or test positive at screening for *C. difficile* toxin or other intestinal pathogens.
7. Subjects receiving the following therapy:
 - Azathioprine/6-mercaptopurine, methotrexate, thalidomide within 7 days prior to baseline.
 - Cyclosporine, mycophenolate, tacrolimus within 4 weeks prior to baseline.
 - Interferon therapy within 8 weeks prior to baseline.
 - Intravenous corticosteroids or rectally administered formulation of corticosteroids or 5-ASA within 2 weeks prior to baseline.
8. Subjects who have previously received JAK inhibitors, such as tofacitinib, baricitinib, upadacitinib, filgotinib. Please discuss with the medical monitor if need clarification.
9. Subjects with evidence of hematopoietic disorders at screening:
 - Hemoglobin levels <9.0 g/dL or hematocrit <30%.
 - An absolute white blood cell (WBC) count of <3.0 x 10⁹/L (<3000/mm³) or Absolute Neutrophil Count (ANC) of <1.2 X 10⁹/L (<1200/mm³).
 - Thrombocytopenia, as defined by a platelet count <100 x 10⁹/L (<100,000/mm³).
10. Subjects with evidence of total bilirubin, aspartate aminotransferase (AST) or alanine aminotransferase (ALT) more than 2 times the upper limit of normal at screening visit. Patients with liver cirrhosis will be excluded.
11. Subjects with eGFR ≤60 ml/min based on Cockcroft-Gault calculation ([Appendix 2](#)), or patient currently undergoes regular haemodialysis.
12. Subjects with current or recent history of severe, progressive, or uncontrolled renal, hepatic, hematological, gastrointestinal, metabolic, endocrine, pulmonary, cardiac, or neurological disease.

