13. Subjects with current clinically significant infections or within 1 month of baseline (e.g. those requiring hospitalization or parenteral antimicrobial therapy or opportunistic infections), or those with a history of more than one episode of herpes zoster, a history (single episode) of disseminated zoster, a history of any infection otherwise judged by the investigator to have the potential for exacerbation by participation in the study or any infection requiring antimicrobial therapy within 2 weeks of screening.
14. Subjects who may have current immunization with any live virus vaccine or history of immunization with any live virus vaccine within 8 weeks of baseline.
15. Subjects with a first-degree relative with a hereditary immunodeficiency.

16. History of any lymphoproliferative disorder (such as EBV-related lymphoproliferative disorder, as reported in some subjects on other immunosuppressive drugs), history of lymphoma, leukemia, myeloproliferative disorders, multiple myeloma, or signs and symptoms suggestive of current lymphatic disease.
17. Any prior treatment with lymphocyte-depleting agents/therapies (such as CamPath® [Alemtuzab], alkylating agents [eg Cyclophosphamide or Chlorambucil], total lymphoid irradiation, etc). Subjects who have received Rituximab or other selective B lymphocyte depleting agents are eligible if they have not received such therapy for at least 1 year prior to baseline.
18. Subjects who have any condition possibly affecting oral drug absorption eg gastrectomy, or clinically significant diabetic gastroenteropathy, or certain types of bariatric surgery such as gastric bypass. (Procedures such as gastric banding, gastric balloon that simply divide stomach into separate chambers, are NOT exclusionary.)
19. Women who are pregnant or lactating, or planning pregnancy while enrolled in the study.
20. History of alcohol or drug abuse with less than 6 months of abstinence prior to baseline.
21. Screening 12-lead ECG that demonstrates clinically relevant abnormalities which may affect subject safety if being enrolled into the study or interpretation of study results.
[\(Appendix 3 ECG exclusion criteria\)](#)
22. Subjects that have donated blood in excess of 500 mL within 2 months prior to baseline.
23. Subjects that have undergone significant trauma or major surgery within 4 weeks of screening visit.
24. Subjects with a temperature of 38°C or higher at screening or baseline.

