25. Subjects with malignancies or with a history of malignancies with the exception of adequately treated or excised non-metastatic basal cell or squamous cell cancer of the skin.
26. Subjects infected with human immunodeficiency virus (HIV) or hepatitis B or C viruses.
27. Subjects who currently suffered from thyroid disorders, including hyperthyroidism, hypothyroidism, or currently on thyroid replacement therapy. Subjects with abnormal TSH, fT4 and fT3 at screening blood check must be excluded.
28. Subjects who have previously participated in any study that received SHR0302.
29. Subjects who have received any investigational drug or device within 3 months prior to baseline.

30. Subjects receiving or are expected to receive prohibited concomitant medication(s) (see [Appendix 4](#)) in the 4 weeks prior to the first dose of study drug.
31. Subjects who, in the opinion of the investigator or Reistone, will be uncooperative or unable to comply with study procedures.
32. Any other condition which in the opinion of the investigator would make the subject unsuitable for inclusion in the study.
33. Subjects with historical or current evidence of clinically significant cardiovascular, neurological, psychiatric, renal, hepatic, immunological, gastrointestinal, urogenital, nervous system, musculoskeletal, skin, sensory, endocrine (including uncontrolled diabetes or thyroid disease) or hematological abnormalities that are uncontrolled. Significant is defined as any disease that, in the opinion of the Investigator, would put the safety of the subject at risk through participation, or which would affect the efficacy or safety analysis if the disease/condition exacerbated during the study.
34. Subjects with a history thrombotic events, including deep vein thromboses (DVT), pulmonary embolism (PE) and those with known inherited conditions that predispose to hypercoagulability.

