6.6.2 Prohibited Medications

The following medications are prohibited throughout the duration of the study:

- azathioprine, 6-mercaptopurine, methotrexate and thalidomide;
- cyclosporine, mycophenolate and tacrolimus;
- interferon and
- anti-TNF α therapy/other biological treatment;
- intravenous corticosteroids or rectally administered formulation of corticosteroids or 5-ASA.
- Oral JAK inhibitors (except the trial medication)

In addition, concomitant administration of CYP3A inducers and moderate to potent CYP3A inhibitors with systemic effects should be avoided for the duration of the study.

Examples of medications that are prohibited from use from 28 days prior to the first dose of study medication until completion of follow up period, due to potential for drug interactions or confounding of data interpretation, are listed in [Appendix 4](#).

All live vaccines immunization are prohibited from signing of informed consent, throughout the duration of the study, and for 1 month after last dose of study medication.

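### Inclusion criterion 4 ties the biologic washout to only one of its two routes of entry, leaving at least 28 to 91 days of the listed intervals unenforced

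*Protocol*

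**What the plan says.** Criterion 4 in Protocol Section 5.2 describes the treatment history a patient must have. The treating physician must judge the patient as "having inadequate response, loss of response or intolerance to the conventional treatment (oral 5-ASA, immune-suppressants or corticosteroids), or previously exposed to anti-TNF therapy" or "other biological treatment (e.g. Vedolizumab) having discontinued the treatment for" the times in a list. The list gives 8 weeks for infliximab, 10 for adalimumab, 14 for ustekinumab and 17 for vedolizumab. It ends with a catch-all: "For the other biological treatments, they should discontinue for a minimum of 5 half-lives prior to baseline".

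Other current rules that deal with earlier treatment are:

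- **Section 5.3, exclusion 7** sets stand-alone washouts for thiopurines, methotrexate and thalidomide, for cyclosporine, mycophenolate and tacrolimus, for interferon ("Interferon therapy within 8 weeks prior to baseline"), and for intravenous or rectal therapy. It has no line for biologics.
- **Exclusion 17** sets an interval for B-cell-depleting agents, whose recipients are "eligible if they have not received such therapy for at least 1 year prior to baseline".
- **Exclusion 29** covers investigational products: "Subjects who have received any investigational drug or device within 3 months prior to baseline".
- **Exclusion 30** bars prohibited medications in the 4 weeks before first dose and refers to Appendix 4, which describes itself as a list of CYP3A inhibitors and inducers.
- **Section 6.6.2** names anti-TNF and other biologics under "The following medications are prohibited throughout the duration of the study". It gives no start date for that ban. A later sentence applies a 28-day period before first dose to examples listed in Appendix 4.

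**The concern.** Read as written, criterion 4 is met by either route. Everyone in the second route is by definition exposed to a biologic, and the washout phrase sits inside that route. The first route, failure of or intolerance to conventional treatment, carries no washout. A patient can satisfy it and also have had a recent biologic dose.

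The sponsor did not intend this. The Amendment No. 02 rationales are used here only as evidence of intent. The rationale for the inclusion change says the discontinuation times were set by the half-life of the biologic. The rationale for the exclusion change says the biologic line was dropped from exclusion 7 because the inclusion criterion now carried the discontinuation requirement. The separate safeguard was therefore removed in reliance on a sentence that does not impose the rule on every exposed patient.

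What is at stake is mainly safety and uniform eligibility. A patient could start a JAK inhibitor with a biologic still on board, in a trial that makes serious infection an adverse event of special interest (Section 7.3.15). Sites could also differ in whether they apply the list.

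The analysis would not reliably reveal such cases. SAP Section 9 lists deviations that have been identified, and the per-protocol set in SAP Section 5.4 depends on a significant violation. A patient who meets criterion 4 literally need not be recorded as either.

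**Working it through.** **Inputs.** The washout weeks come from Protocol Section 5.2, criterion 4. The screening window of day -28 to day -1 comes from Section 4.2. The 28-day and 4-week rules come from Section 6.6.2 and exclusion 30.

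**Step 1: listed intervals in days (weeks × 7).** Infliximab 8 × 7 = 56; adalimumab 10 × 7 = 70; ustekinumab 14 × 7 = 98; vedolizumab 17 × 7 = 119.

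**Step 2: which other rule could bind a patient entering by the first route.** Exclusion 7 has no biologic line. Exclusions 17 (1 year) and 29 (3 months) are long enough to matter, but they do not cover ordinary use of the four named drugs. That leaves Section 6.6.2 and exclusion 30, which can be read in three ways:

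- **Reading A.** The 28-day sentence and exclusion 30 are stretched to include biologics, on the ground that Appendix 4 gives only examples. Floor: 28 days. This is generous, because Appendix 4 is a CYP3A list.
- **Reading B.** The during-study ban on biologics starts at consent, 1 to 28 days before baseline. Floor: 1 to 28 days.
- **Reading C.** The ban starts at baseline and the 28-day rule is limited to Appendix 4 drugs. Floor: 0 days.

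Section 6.6.2 does state a start point for live vaccines (signing of consent) but none for biologics, so the text does not settle the choice between B and C.

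**Step 3: shortfall = listed interval − floor.**

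| Drug | Listed (days) | Reading A | Reading B | Reading C | Share covered under A |
|---|---|---|---|---|---|
| Infliximab | 56 | 56 − 28 = 28 | 28 to 55 | 56 | 28/56 = 50% |
| Adalimumab | 70 | 70 − 28 = 42 | 42 to 69 | 70 | 28/70 = 40% |
| Ustekinumab | 98 | 98 − 28 = 70 | 70 to 97 | 98 | 28/98 = 29% |
| Vedolizumab | 119 | 119 − 28 = 91 | 91 to 118 | 119 | 28/119 = 24% |

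For other biologics the interval is 5 half-lives. The documents give no half-lives, so that shortfall cannot be computed.

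**Step 4: after correction.** If the washout applies to every exposed patient, the minimum intervals are 56, 70, 98 and 119 days and the shortfall is 0. Sample size, alpha and planned power do not change.

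No power loss is calculated. The fraction of patients who might enter this way is not in the documents, and neither is the direction in which residual biologic would move Week 8 response.

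**The case against.** The strongest reply is that this is loose drafting which no sensible site would exploit. Anyone recently given one of the four drugs is plainly previously exposed. The drug-by-drug list was written for that patient, and its last bullet reads as a free-standing instruction. The amendment rationale is bound into the same protocol and shows how the criterion should be read; under that reading the shortfall is zero. Prior exposure also has to be declared for stratification (Section 6.2), medications are reviewed at screening and baseline (Section 5.12), eligibility is documented (Section 5.1), and exclusion 32 lets the investigator refuse a patient. The documents do not state why the intervals were chosen beyond half-life, so avoiding confounding of efficacy is as possible a purpose as safety.

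Much of this stands. Many sites would probably apply the list, and nothing shows that an unwashed patient was or would be enrolled. The listed controls make exposed patients visible. Inclusion 2 (active disease), stratified randomization and analysis, exclusion 13 on infections, withdrawal for serious infection (Section 5.6) and the safety committee reviews (Section 5.11) limit the consequence. The day counts measure a gap in the rules and not an effect on patients or results.

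It does not close the gap. None of these controls is a washout: stratification records whether a patient was ever exposed and not how recently, and the others are discretionary or act after enrolment. The evidence of intent shows what the criterion should require; its wording still admits patients the sponsor meant to keep out.

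**Conclusion.** The concern holds and should be fixed. Criterion 4, followed literally, imposes no biologic washout on a patient who qualifies through failure of conventional treatment, and no other current rule supplies the listed intervals. The shortfall is 28, 42, 70 and 91 days under the most generous reading and the full 56, 70, 98 and 119 days under the strictest.

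This rests on reading the or as separating two sufficient routes and on the washout phrase belonging to the second. Confidence is high that the gap in the text exists. Its practical effect may be small: the number of patients affected is not given, and no claim is made about bias or power.

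**What to change.** Keep criterion 4 for treatment history and make the washout a separate condition, for example: *and, if the patient has ever received a biologic, that treatment was stopped for at least the following time before baseline*, followed by the same list. Restoring a biologic line with those intervals in exclusion 7 would serve equally well. The cost is one sentence in an amendment and a clarification memo to sites. The downside is that a few recently treated patients would wait or not be enrolled, as the sponsor already intended.

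Enrolment may already be complete: SAP Section 3.3 refers to data before the interim lock, and SAP Section 4.2 places that analysis after all patients could have reached Week 8. In that case, use the medication end dates that SAP Section 12 already plans to list. Produce one listing of days from last biologic dose to baseline and flag anyone below the relevant interval. First confirm that medication history was collected at least 119 days back, since the documents do not state the look-back. For biologics outside the four named, the half-life used should be recorded with the flag.
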